$$\text{TWA-SaO}_2 = [(SaO_{2a} * \text{Time a}) + (SaO_{2b} * \text{Time b}) + \dots (SaO_{2z} * \text{Time z})] / (\text{Time a} + \text{Time b} + \dots \text{Time z})$$

We will build a multivariable regression model to test the association between TWA-PaO₂ and mRS at hospital discharge, adjusting for covariates previously demonstrated to be associated with poor neurological outcome after cardiac arrest. Covariates to be considered include: (1) pre-arrest comorbidities (Charlson index⁶⁹), (2) prolonged downtime (downtime > 20 minutes) (yes/no), (3) initial arrest rhythm (pulseless electrical activity/asystole vs. ventricular tachycardia/ventricular fibrillation), and (4) arrest location (in-hospital vs. out-of-hospital).⁷⁰⁻⁷⁵ In addition, in order to account for patients with lung injury (i.e. inability to maintain adequate oxygenation) we will add PaO₂/FiO₂ < 100mmHg (yes/no) to the regression model. We will build separate models to test the association between TWA-PaO₂ (adjusting for the five covariates above) and each of the five cognitive domains in our neuropsychological testing. We will then repeat these analyses using TWA-SaO₂ as the exposure variable of interest. This approach will not only allow us to test for an independent association between the exposure and neurological disability and neuropsychological deficits, but will also allow us to pinpoint one or more types of cognitive deficit (e.g. attention, executive function) most closely associated with the exposure. Given outcome measures that are quantitative (i.e. z-score for each cognitive domain) or semi-quantitative (i.e. mRS at hospital discharge), we will treat these outcomes as *continuous* dependent variables for modeling. Using continuous measures of the exposure and outcomes (rather than collapsing the data into categorical variables) will permit detection of subtle effects that could be missed if only categorical analyses were employed.

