Secondary analyses: We will compare proportions of good neurological outcome [defined as a mRS ≤ 3 (based on the preliminary data of our collaborator, [name], University of Pittsburgh)],⁴⁵ between subjects who receive the study intervention (i.e. rapid FiO₂ optimization) vs. those who do not receive the study intervention, using binomial test. Among survivors, we will compare the 180-day neuropsychological measures (composite z-scores for each cognitive domain) between the same two groups using t-test or Mann-Whitney U as appropriate with corrections for multiple comparisons. We will compare the proportions of patients able to return to work between the two groups using binomial test. We will compare plasma IsoPs/IsoFs at each time point between the two groups using t-test or Mann-Whitney U as appropriate with corrections for multiple comparisons.

Sample Size: The sample size calculation in the initial study proposal was based on the primary outcome, mRS at hospital discharge, and we planned to enroll a total of 266 subjects. To ensure adequate power to test the relationships between the above independent variables and cognitive domains, we assumed a medium relationship strength between the six independent variables and each of the five cognitive domains ($R^2 = 0.15$). In order to achieve 80% power and an $\alpha = 0.05$ we would require a minimal of 85 subjects to undergo neuropsychological testing at 180 days. This sample size will be among the largest prospective studies of

neuropsychological outcomes that we are aware of in the literature.^{8,29-32} Assuming a 15% drop out rate for lost to follow up for neuropsychological testing at 180 days we would require 98 subjects to be discharged with a mRS \leq 4. Based on preliminary data from REOX I we expect 35% of patients will be discharged with a mRS \leq 4 and undergo cognitive testing at 180 days. We would therefore require a minimal total sample size of 280 subjects between REOX I and II combined for the multivariable testing. We have enrolled 200 subjects in REOX I to date. We anticipate additional subjects to be enrolled in REOX I and therefore plan for 75 subjects to be enrolled in REOX II to ensure a total sample size of at least 280 subjects.

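### The 80% power at 85 tested subjects belongs to the joint six-predictor test, not to the adjusted oxygen-exposure coefficient that the plan will test

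*Combined protocol and SAP*

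**What the plan says.** The Sample Size paragraph of section D.2 gives its purpose as "To ensure adequate power to test the relationships between the above independent variables and cognitive domains". Its assumption is that "we assumed a medium relationship strength between the six independent variables and each of the five cognitive domains", with R² = 0.15. At 80% power and alpha 0.05 it concludes that "we would require a minimal of 85 subjects to undergo neuropsychological testing at 180 days". An allowance of 15% for loss to follow-up takes 85 to 98 subjects discharged with an mRS of 4 or less. The plan expects 35% of patients to be discharged in that state "and undergo cognitive testing at 180 days", and so arrives at the total: "We would therefore require a minimal total sample size of 280 subjects between REOX I and II combined for the multivariable testing".

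The Analysis part of D.2 describes the models that will be fitted. There is one model per cognitive domain for TWA-PaO₂, "adjusting for the five covariates above) and each of the five cognitive domains in our neuropsychological testing". After that, "We will then repeat these analyses using" TWA-SaO₂. The declared aim is to "test for an independent association between the exposure and neurological disability and neuropsychological deficits".

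No section gives an effect size for the exposure alone, whether as a slope, a partial R² or a unique R². Section D.1.2 lists the 180-day neuropsychological tests as secondary outcomes.

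**The concern.** The assumption behind the 85 is a single R² shared by six predictors: the oxygen exposure and five covariates. The power that goes with it is the chance of showing that the six together explain something. The scientific question in each domain model is whether the exposure explains something after the other five are accounted for, which is a test of one coefficient on one degree of freedom.

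The two can diverge widely. The covariates were chosen because earlier work links them to poor neurological outcome. If they alone supplied the R² of 0.15, the joint test would still be significant about four times in five, while the exposure coefficient would be significant only at the 5% false-positive rate.

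This matters because the 85 leads to 98 and then to 280, so the power offered in support of the current total belongs to a test that the Analysis section does not describe. A null TWA-PaO₂ result in a domain could then be read against 80% power that the test may not have had. The point is limited to the 180-day cognitive-domain models. It does not concern the discharge mRS model or the comparisons between patients who did and did not receive the protocol.

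**Working it through.** **Inputs from D.2.** Alpha 0.05; power 80%; full-model R² = 0.15; six predictors (the exposure, Charlson index, prolonged downtime, initial rhythm, arrest location, and PaO₂/FiO₂ below 100 mmHg); 85 tested. **Not in the documents:** the exposure's unique R², meaning the rise in R² when it is added to the five covariates. A range of 0.025 to 0.10 is assumed below; 0.025 is an equal sixth of 0.15.

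**Step 1: reproduce the 85.** For the overall F-test, u = 6, v = N − 7, f² = 0.15/0.85 = 0.1765 and λ = f²N. Power is 79.6% at N = 83, 80.2% at 84 and 80.8% at 85. Other readings miss the stated figure:
- taking the medium effect as f² = 0.15 needs 98;
- a one-coefficient test with the whole 0.15 as the exposure's partial R² needs 47.

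The stated 85 is therefore the overall-test figure, and it is correct for that test.

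**Step 2: power for the exposure coefficient at 85 tested.** Now u = 1, v = 85 − 7 = 78, f² = (unique R²)/(1 − 0.15) and λ = 85f². With random (multivariate normal) predictors, λ = f²W with W distributed as chi-square on 79 degrees of freedom, and power is averaged over W.

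| Unique R² (assumed) | f² | λ (fixed) | Power, fixed | Power, random |
|---|---|---|---|---|
| 0.025 | 0.0294 | 2.5 | 35% | 33% |
| 0.05 | 0.0588 | 5.0 | 60% | 56% |
| 0.075 | 0.0882 | 7.5 | 77% | 73% |
| 0.10 | 0.1176 | 10.0 | 88% | 84% |

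**Step 3: the effect detectable with 80% power at 85 tested.**
- Fixed predictors: f² = 0.0947. Unique R² = 0.0947 × 0.85 = 0.080; partial R² = 0.0947/1.0947 = 0.086. Share of explained variance: 0.0805/0.15 = 54%.
- Random predictors: f² = 0.1041. Unique R² = 0.088; partial R² = 0.094. Share: 0.0884/0.15 = 59%.

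**Step 4: sensitivity to the number tested.** The text can be read as 98 × 0.85 = 83 tested, or, taking the 35% literally as the tested fraction, 280 × 0.35 = 98. Partial R² is used here because its threshold does not depend on the full-model R².

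| Tested | Partial R² for 80%, fixed | Partial R² for 80%, random |
|---|---|---|
| 83 | 0.088 | 0.097 |
| 85 | 0.086 | 0.094 |
| 98 | 0.076 | 0.082 |

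**Step 5: sensitivity to the full-model R².** At 85 tested, the unique R² needed is f² × (1 − R²). Fixed / random, this is 0.085 / 0.094 at R² = 0.10, 0.076 / 0.083 at 0.20 and 0.066 / 0.073 at 0.30.

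**Step 6: simulation check.** With 20,000 data sets per point, 85 subjects, six independent normal predictors and R² = 0.15, the coefficient was significant in 5.0%, 32.6%, 56.5%, 75.8% and 80.7% of runs at unique R² of 0, 0.025, 0.05, 0.08 and 0.09. The overall test stayed at 79% to 80% throughout, including where the exposure contributed nothing.

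**The case against.** The strongest reply is that the paragraph claims no more than it calculates. It speaks of relationships with the independent variables in the plural, attaches the R² to all six, and never says that TWA-PaO₂ alone has 80% power. That is a fair reading of the words, but it leaves the mismatch in place: the joint relationship is what was powered, and the exposure's independent association is what the Analysis section sets out to test.

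A second reply is that no shortfall has been shown. This stands. The exposure's share of R² is not in the documents, nothing there makes 0.025 more plausible than 0.09, and above roughly 0.08 to 0.09 the 85 is enough.

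Third, 85 is presented as a minimum. If 98 are tested, the unique R² needed at full-model R² of 0.15 falls to 0.070 (fixed) or 0.075 (random). This also stands, and it is why a range is given. The opposite reading, 83 tested, raises the threshold only slightly.

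Fourth, the covariates are listed for consideration, so the final set may differ, and most are binary, so the normal-predictor figures are approximate. True, but the fixed and random thresholds differ by no more than about 0.01 in R², and the conclusion does not rest on the third decimal.

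Finally, these are secondary outcomes. They are, but they are the stated basis of the total of 280.

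**Conclusion.** The concern holds and should be fixed. The 85 and its 80% are arithmetically sound for the overall six-predictor test at R² = 0.15. They do not describe the adjusted TWA-PaO₂ or TWA-SaO₂ coefficient, which is the planned test in each cognitive-domain model. At 85 tested and two-sided alpha 0.05, that coefficient has 80% power only for a partial R² of about 0.09, equivalent to a unique R² of 0.080 to 0.088 if the full model explains 15%. The exposure would then carry 54% to 59% of everything the six predictors explain.

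Whether power is inadequate depends on an exposure effect that the plan does not state: across the assumed unique R² of 0.025 to 0.10 it runs from about one in three to 84–88%. All figures use alpha 0.05 for each model, with no adjustment across the five domains or the two exposures.

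**What to change.** Reword the Sample Size paragraph so that the 80% is attributed to the overall test of six predictors at R² = 0.15 and is no longer offered as securing power for the exposure test. Then add the detectable effect for the adjusted exposure coefficient in a domain model: at two-sided alpha 0.05, 80% power requires a partial R² of about 0.09 with 85 tested, or about 0.08 to 0.10 as the number tested runs from 98 down to 83. Say whether predictors were treated as fixed or random and, if a unique R² is quoted, which full-model R² was assumed.

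The cost is wording only. No patients are added and the total of 280 is unchanged. The stated figure becomes less favourable, and the sponsor may be asked what share of R² it expects from oxygen exposure.

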- *Reduced neurological disability at hospital discharge (Aim 2)*
- *Reduced neuropsychological and functional deficits among survivors at 180 days (Aim 3)*

D.1.2. Overview

Design: Prospective protocol implementation study with an observational comparison group [REOX II (intervention component) versus REOX I (observational component)]

Participants: Adult patients resuscitated from cardiac arrest

Enrollment location: Emergency Departments of 6 urban academic medical centers

Intervention: Implementation of a clinical protocol for rapid FiO₂ optimization after ROSC from cardiac arrest.

Primary outcome: Good neurological outcome (defined as Modified Rankin Scale ≤ 3 ⁴⁵ at hospital discharge).

Secondary outcomes: Neuropsychological tests and ability to return to work among survivors at 180 days.

Mechanistic outcomes: Oxidative stress markers (IsoPs/IsoFs) in plasma 0-6 hours after ROSC.

Estimated sample size and study duration: 280 patients (205 from REOX I and 75 from REOX II).

[figure not shown]
D.2. REOX II Study Protocol

Study setting and population: This study is the second phase in a two-phase study. The initial phase, REOX I, was an observational-only study. As in REOX I, REOX II will identify subjects with return of spontaneous circulation (ROSC) after cardiac arrest in 6 hospitals (Cooper University Hospital, Camden, NJ; Hospital of the University of Pennsylvania and Penn-Presbyterian Medical Center, both in Philadelphia, PA; University of Mississippi Medical Center, Jackson, MS; Methodist Hospital, Indianapolis, IN; and Beth Israel Deaconess Medical Center, Boston, MA). The inclusion criteria are: age > 17 years; cardiac arrest; ROSC achieved; comatose (Glasgow Coma Scale motor score < 6) after ROSC; and clinician intent to treat with target temperature management. The exclusion criteria are: presumed etiology of arrest is trauma, hemorrhage or sepsis; resident of a nursing home or other long-term care facility; known or clinically apparent pregnancy; known lack of commitment to aggressive support by next of kin; and any other condition, that, in the opinion of the investigator, would preclude the subject from being a suitable candidate (e.g. end stage chronic illness with no reasonable expectation of survival to hospital discharge).

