Patient identification and recruitment: Each of the participating centers currently has a mechanism in place for real-time notification of study personnel when an OHCA subject arrives in the emergency department (ED) or when a cardiac arrest occurs in-hospital. Each center has previously validated its notification mechanism to ensure that subjects will not be missed and the population of potentially eligible subjects will be consecutive cardiac arrest subjects. Study personnel will assess patient eligibility and will immediately enroll subjects meeting all inclusion and no exclusion criteria.

Informed consent: In line with REOX I (observational-only component), in REOX II we will begin initial collection of cardiac arrest and post-resuscitation data immediately after ROSC. As per the inclusion criteria all subjects will be comatose during the initial post-ROSC period and therefore will not be able to consent themselves for the study intervention (i.e. protocol for rapid FiO₂ optimization after cardiac arrest). Once a subject is identified to have all inclusion and no exclusion criteria, we will approach surrogates (i.e. next of kin or legally authorized representative)

Figure 9 Flow diagram for enrollment

[figure not shown]
within the first four hours after ROSC for written informed consent and HIPAA authorization prior to implementation of the study intervention. If communication with a surrogate within the first four hours after ROSC is not achieved the subject will not be eligible for the study intervention. However, for subjects who are excluded from the study intervention due to lack of informed consent within the first four hours after ROSC, we will approach subjects or surrogates at a later time for written informed consent and HIPAA authorization for participation in the observational only (REOX I) component of the study including (a) use of plasma samples for research purposes (both stored samples obtained at the time of initial resuscitation and new samples); (b) determination of Modified Rankin Scale at hospital discharge; and (c) follow-up visits for neuropsychological testing at 180 days (**Figure 9**).

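### The 15% dropout allowance was multiplied on (85 × 1.15 = 98) instead of divided out (85/0.85 = 100), so the minimum of 280 is expected to give about 83 tested at 180 days, not 85

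*Combined protocol and SAP*

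**What the plan says.** The Sample Size paragraph (section D.2) sizes the combined cohort on the 180-day neuropsychological models. It assumes R² = 0.15 for six independent variables, 80% power and α = 0.05, and concludes "we would require a minimal of 85 subjects to undergo neuropsychological testing at 180 days". Three steps follow:

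- Dropout: "Assuming a 15% drop out rate for lost to follow up for neuropsychological testing at 180 days we would require 98 subjects", these being patients discharged with mRS ≤ 4.
- Yield: "Based on preliminary data from REOX I we expect 35% of patients will be discharged with a mRS" score of at most 4. The sentence then attaches a second condition to the same 35%, in the words "and undergo cognitive testing at 180 days".
- Total: "We would therefore require a minimal total sample size of 280 subjects between REOX I and II combined for the multivariable testing".

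It reports 200 subjects already in REOX I, anticipates more, and sets a "plan for 75 subjects to be enrolled in REOX II to ensure a total sample size of at least 280 subjects". The Overview (section D.1.2) gives the same total: "280 patients (205 from REOX I and 75 from REOX II". The paragraph also mentions an initial total of 266, based on mRS at discharge.

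**The concern.** A dropout rate is a fraction of those who could be followed up, so the number to start with is the target divided by one minus the rate. Adding 15% to the target gives too small a number. Here the stated 98 falls below the plan's own minimum once its own 15% is taken off, and the error carries into the total of 280.

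There is also a disagreement between words and arithmetic. Dividing 98 by 0.35 treats the 35% as the share discharged with mRS ≤ 4, before follow-up losses. The sentence describes the 35% as discharged and also tested, which would already include those losses.

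At stake is whether the figure offered as the minimum for the multivariable models delivers the 85 tested and the 80% power claimed for it. Only the 180-day models are affected.

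**Working it through.** **Inputs, all from the Sample Size paragraph:** 85 tested; 15% dropout; 35% yield; total 280; R² = 0.15; six predictors; α = 0.05; power 80%. The paragraph does not name the test. I assume the overall F test of the regression, which fits the stated inputs.

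**1. The 85.** With f² = 0.15/0.85 = 0.176, noncentrality N × f², and 6 and N − 7 degrees of freedom:

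| N tested | Power |
|---|---|
| 83 | 79.6% |
| 84 | 80.2% |
| 85 | 80.8% |
| 98 | 87.3% |

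The smallest N reaching 80% is 84, so 85 is sound. The fault lies in what follows.

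**2. The 98.**
- Multiplying: 85 × 1.15 = 97.75, rounded up to 98. This reproduces the plan.
- Dividing: 85/(1 − 0.15) = 100.
- Check: 98 × 0.85 = 83.3 tested, below 85. Going from 98 to 85 is a loss of 1 − 85/98 = 13.3%, not 15%.

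**3. The 280, with 35% as the share discharged with mRS ≤ 4.**
- 98/0.35 = 280 exactly. This reproduces the plan.
- Expected tested: 280 × 0.35 × 0.85 = 83.3.
- Corrected total: 100/0.35 = 285.7, so 286. Check: 286 × 0.35 × 0.85 = 85.1.
- With 280 kept, 85 tested is reached only if the discharge share is at least 100/280 = 35.7% or dropout is at most 13.3%.

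**4. The 280, with 35% as the share discharged and tested.**
- Expected tested: 280 × 0.35 = 98, with 87.3% power.
- The 15% has then been allowed for twice. The total needed is 85/0.35 = 242.9, so 243.

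**5. The two readings compared.** The first leads from 85 to 286 and the second from 85 to 243. Neither gives 280.

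**The case against.** The strongest case is that the effect is negligible.

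- *Size.* Against the 80% target, 84 tested would do, so the expected 83.3 is 0.7 of a subject short and power at 83 is 0.4 points short. An expected 84 needs 283 in total (283 × 0.35 × 0.85 = 84.2).
- *Noise in the inputs.* The 35% is preliminary and the 15% is an assumption. If the number tested is binomial with probability 0.35 × 0.85 = 0.2975, its standard deviation at 280 is √(280 × 0.2975 × 0.7025) ≈ 7.6. The chance of at least 85 is about 43% at 280 and 53% at 286.
- *Slack in the wording.* The plan says at least 280 and expects more REOX I enrolment. The Informed consent text keeps REOX I open by approaching patients without timely consent for "participation in the observational only (REOX I) component of the study".
- *The shortfall is conditional.* On the literal wording of the 35% there is none.
- *The testing pool.* The Outcome measures text offers testing to everyone discharged alive, so some survivors with mRS 5 might add to the count.
- *The test.* The power figures are for the overall F test, whereas the models are meant to examine the oxygen exposure adjusted for five covariates.

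The points on size and noise stand, and they are why this is a correction to the text and not a threat to the study. They do not make 98 or 280 follow from 85. The slack makes the remedy easy, but the Overview budgets exactly 205 + 75 = 280, and nothing commits to more. The literal reading removes the shortfall only by making the 15% redundant, so the paragraph needs correcting either way. The wider testing pool does not alter a chain that the plan builds on mRS ≤ 4, and the plan gives no figure for what it might add. The last point is a fair limit: moving from 280 to 286 says nothing about power for the exposure coefficient alone.

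**Conclusion.** The concern holds. The dropout allowance was applied the wrong way, and the stated minimum of 280 does not follow from the plan's own inputs. If the 35% is the discharge share, as the plan's division implies, 280 falls about 2 tested patients short of 85, and power of the overall test drops by about 1 point to 79.6%, just under the 80% stated. If the 35% already includes testing, 280 exceeds the need by 280 − 243 = 37 subjects. The documents do not settle which applies; the REOX I data behind the 35% would.

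The power figures assume the overall F test with R² = 0.15 and six predictors. The effect is confined to the 180-day neuropsychological models. It does not touch mRS at discharge or require a change to the 75 in REOX II.

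**What to change.** First state whether the 35% is the share discharged with mRS ≤ 4 or the share discharged and tested.

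- If it is the discharge share, delete the reference to testing from that sentence. Then do one of two things:
  - keep 280 and state that it is expected to give about 83 tested, with just under 80% power for the overall test; or
  - restate the chain as 85 tested, 100 discharged, 286 in total.
- If it is the discharged-and-tested share, remove the separate 15% step and give the total that follows (243), or keep 280 and present the excess as a margin.

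Keeping 280 costs wording only. Adopting 286 also means updating the Overview total. The 6 extra subjects can come from REOX I, which would then supply 286 − 75 = 211 instead of 205, with the 75 unchanged.

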Figure 5 (left): Proportions of in-hospital mortality and independent functional status among survivors over increasing oxygen tensions. We found linear trends for increasing mortality and decreasing functional independence with increasing oxygen tension, $p < 0.0001$.

Figure 6 (right): Odds ratios (solid line) and 95% confidence intervals (dotted lines) for in-hospital death with increasing increments of oxygen tension.

C.3.3. Development of a clinical protocol for rapid FiO₂ optimization.

The method of rapid FiO₂ optimization in REOX II must be comprised of a detailed protocol (see *Methods* section below) rather than a simple directive to titrate FiO₂ to keep SaO₂ or PaO₂ in a predetermined range, because rigorous uniformity is needed in the approach across all study sites, including uniformity in the increments and frequency of FiO₂ reductions. The therapeutic goal of our protocol is a PaO₂ of 60-99 mmHg, because this is the PaO₂ range that was associated with the lowest risk of poor outcome in our previously published work.²⁵ We also use PaO₂ (measured by arterial blood gas [ABG] analysis) as the ultimate goal rather than SaO₂ measured by pulse oximetry because an SaO₂ value <100% on pulse oximetry monitoring does not always exclude supranormal PaO₂. The protocol in this application begins with very rapid reduction of FiO₂ as much as possible according to SaO₂ values, and when FiO₂ is maximally reduced by SaO₂ an ABG is measured, followed by finer adjustment of FiO₂ to achieve a PaO₂ 60-99 mmHg. The protocol must not only prescribe each downward titration of FiO₂ but it must also include detailed limbs for *upward* titration of FiO₂ to account for potential “overshoot” in FiO₂ reduction. We acknowledge that the flowchart for FiO₂ titration in the *Methods* section (**Figure 9**) may appear complex, but our experience is that this level of detail is needed in order to ensure that FiO₂ optimization will not only be rapid and effective, but also safe. We believe using this protocol will allow for rapid achievement of the target PaO₂ after ROSC and no significant hypoxic events related to overshoot.

C.3.4. Optimal assessment of oxidative stress *in vivo*.

Roberts LJ, and colleagues. Biomarkers of Oxidative Stress Study II: Are oxidation products of lipids, proteins, and DNA markers of CCL₄ poisoning? *Free Radic Biol Med* 2005;38(6):698-710.

[figure not shown]

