Overview of the safety monitoring plan and serious adverse event tracking: In order to help ensure adequate protection of human subjects enrolled in this clinical study, we established an independent three-member **Data Safety Monitoring Board (DSMB)** (see **DSMB Charter**). The Chair of the DSMB will be [name]. [name] is an established investigator and is currently the Director of Clinical Research, Department of Emergency Medicine, Cooper University Hospital, Camden, NJ. The DSMB will be charged with reviewing all serious adverse event reports and will also perform interim analysis of the data after one-third (n=25) and two-thirds (n=50) of the patients have been enrolled in REOX II. Given neither REOX I nor REOX II are blinded, all data reviewed by the DSMB will be unmasked. At both interim analyses the committee will be asked to render a decision as to whether the trial should be continued, modified, or stopped based on the safety profile of the interim data. We have defined the following *a priori* as a reportable serious adverse event (SAE): (1) any events resulting in death or repeat cardiac arrest; (2) sustained hypoxia (defined as $\text{SaO}_2 < 88\%$ for more than three consecutive minutes); (3) heart rate < 50 for greater than one minute; (4) documented cyanosis at any time; or (5) withdrawal of a subject from the trial for any reason. We will define excessive rates of any single SAE *a priori* as a $>15\%$ difference in the prevalence (% of total number in each group) between the two groups [i.e. subjects who receive the study intervention (i.e. rapid FiO_2 optimization) vs. those who do not receive the study intervention] at either interim analysis. A clinician can withdraw a subject from the study for worsening clinical status including worsening respiratory status (based on clinical judgment, arterial blood gas analysis, or increasing FiO_2 requirement). The site PIs at each collaborating institution will be responsible for reporting all predefined SAEs, as well as any other adverse events felt to be related to the study protocol, to the coordinating site, Cooper University Hospital. In addition to reporting all adverse events to the DSMB, all adverse events will be submitted to each institution's IRB for review.

Registration: This study will be registered on clinicaltrials.gov

References

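### The 15-point safety flag is applied to each SAE singly, so a respiratory excess spread over hypoxia, cyanosis and withdrawal can go unflagged; a pooled flag is a cheap addition

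*Combined protocol and SAP*

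**What the plan says.** All of this is in D.2, under the overview of the safety monitoring plan, unless stated otherwise.

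- The DSMB performs an "interim analysis of the data after one-third (n=25) and two-thirds (n=50) of the patients have been enrolled in REOX II".
- Five reportable SAEs are listed. Three can register respiratory worsening: "2) sustained hypoxia" (SaO2 below 88% for more than three consecutive minutes), "4) documented cyanosis at any time" and "5) withdrawal of a subject from the trial for any reason".
- The limit is set per event type: "We will define excessive rates of any single SAE" is followed by "as a $>15\%$ difference in the prevalence (% of total number in each group". The comparison is between those who receive the FiO2 protocol and those who do not. No pooled limit appears.
- Withdrawal has a respiratory route with no SaO2 threshold: "A clinician can withdraw a subject from the study for worsening clinical status including worsening respiratory status". The grounds are clinical judgment, blood gases or a rising FiO2 requirement.
- Site PIs report every predefined SAE. The DSMB reviews all SAE reports and decides on the safety profile as a whole. A DSMB Charter is cited.
- The data collection paragraph of D.2 plans continuous SaO2 capture for the first 36 hours after ROSC. It does not mention withdrawn subjects.
- C.3.3 identifies overshoot in FiO2 reduction as the hazard to guard against, and expects "no significant hypoxic events related to overshoot".

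**The concern.** The foreseeable harm of this intervention is too little oxygen. Depending on timing, that harm may meet one, two or all three of the respiratory definitions. A patient withdrawn before the three-minute criterion is met may count only as a withdrawal, and brief cyanosis may count only as cyanosis. The limit is never applied to the number of patients with any of these events, so each part can stay at or below 15 points while the total is above it.

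The division is also uneven between groups. REOX I patients had clinician-directed FiO2 and no FiO2 protocol to be withdrawn from, so respiratory withdrawal arises essentially only in REOX II. At stake is whether the one numerical trigger in the plan responds to the hazard the plan itself names.

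**Working it through.** **Inputs from the documents.** REOX II is planned at 75 (Sample Size; D.1.2), so the looks fall at 75/3 = 25 and 2 × 75/3 = 50, as stated. REOX I is planned at 205 (D.1.2). I read the limit as more than 15 percentage points, in the direction of more events in REOX II. The plan gives no derivation of the 15% and no event rates, so every rate below is an assumption.

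**Step 1: counts.** Take a comparison rate of 0%.

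- n=25: 0.15 × 25 = 3.75, so 3 patients (12%) per category raise no flag. Over three categories with no overlap that is 9/25 = 36%.
- n=50: 0.15 × 50 = 7.5, so 7 patients (14%) per category raise no flag. Over three categories that is 21/50 = 42%.
- A pooled count with the same limit flags at 4/25 or 8/50 (16% each).

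These are no-overlap worst cases. They show what the wording permits, not what is likely.

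**Step 2: chance of a flag when hypoxia and withdrawal share the harm.** Assume 10% harm in REOX I, all recorded as SAE 2, and 30% in REOX II, with one third of the affected withdrawn first. Let k be the share of those withdrawn who are still counted under SAE 2.

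- C ~ Bin(205, 0.10); T ~ Bin(n, 0.30); W given T ~ Bin(T, 1/3); K given W ~ Bin(W, k).
- Written rule: (T − W + K)/n − C/205 > 0.15, or W/n > 0.15.
- Pooled rule: T/n − C/205 > 0.15.

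The expected SAE 5 rate is 30% × 1/3 = 10% against 0%. The expected SAE 2 rate in REOX II is 20% + 10% × k, so the SAE 2 excess is 10, 15 or 20 points for k = 0, 1/2 or 1. The true total excess is 20 points.

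| Withdrawn patients also counted under SAE 2 | Written rule, n=25 | Written rule, n=50 | Pooled, n=25 | Pooled, n=50 |
|---|---|---|---|---|
| none | 46% | 31% | 69% | 76% |
| half | 58% | 54% | 69% | 76% |
| all | 71% | 77% | 69% | 76% |

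With k = 0 the written rule becomes less likely to fire as data accumulate, because each expected excess (10 points) is below the limit. With k = 1 it is marginally above the pooled rule, because a chance excess of withdrawals can also trigger it. Over both looks with k = 0, the figures are 53% as written and 83% pooled.

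**Step 3: three categories, including cyanosis.** Assume a 6% pooled rate in REOX I and a 20-point excess.

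- Equal split over three categories with no overlap: written rule 24% / 10% (n=25 / n=50), pooled 71% / 78%.
- Half of affected patients in all three categories and half in one only: written rule 60% / 57%, pooled 70% / 78%.
- Every affected patient in all three: the two rules are identical.

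**Step 4: sensitivity of step 2, with k = 0.**

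- 10% v 30%, half withdrawn: written 59% / 51%, pooled 69% / 76%.
- 5% v 25%, one third withdrawn: written 44% / 32%, pooled 71% / 79%.
- 15% v 35%, half withdrawn: no gain from pooling at n=25, about 7 points at n=50.

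**Step 5: false flags.** With 10% in both groups and no extra withdrawals, the pooled rule fires in 1.7% / 0.2%. Now add 5% independent respiratory withdrawals in REOX II only. The pooled REOX II rate becomes 1 − 0.90 × 0.95 = 14.5%. The pooled rule then fires in about 9% / 3%, against 5% / 0.5% for the written rule.

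**The case against.** The strongest reply is that the SAE categories are not exclusive. Sites report every predefined SAE, so a patient who is hypoxic, cyanotic and withdrawn counts under all three. With full overlap the written rule loses nothing. This stands, and it makes the size of the problem conditional.

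Three stronger readings are tempting, and the documents do not support them.

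- A reader might infer that a withdrawn patient drops out of SAE 2 counting. Nothing says so. SaO2 capture is planned for 36 hours with no exception for withdrawal, and data are collected on patients who never receive the intervention. But withdrawal is described as being from the study, and nothing says that capture continues. The text is silent, and the first row of the step 2 table is one end of a range.
- A reader might infer that prompt withdrawal hides hypoxia. A patient withdrawn before the three-minute criterion is met has not had the defined event, and the hypoxia may really have been averted. SAE 5 still records the withdrawal.
- A reader might infer that the DSMB would miss the excess. The 15% definition is not written as a stopping rule. The board sees unmasked data and every SAE report, judges the overall profile, and can read the three rows together. The charter may also hold a pooled rule.

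It is also fair that a pooled flag containing withdrawals is asymmetric between the groups, as step 5 shows. That bears on how the flag is presented. It does not remove the case for having one.

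**Conclusion.** This is a cheap improvement to the pre-specified trigger. It does not show that safety oversight fails. The wording allows a respiratory excess above 15 points in total with no single SAE flagged. In the main scenario (10% v 30%, one third withdrawn, 205 comparators), the loss against a pooled measure is 69 − 46 = 23 points at n=25 and 76 − 31 = 45 points at n=50 with no overlap. It is 11 and 22 points with half overlap, and nil with full overlap. All rates and the degree of overlap are assumptions. The conclusion also depends on the charter: if it already contains a pooled respiratory rule, the protocol need only refer to it.

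**What to change.** In the safety monitoring paragraph of D.2:

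1. Keep the single-SAE comparisons as they are.
2. Add a pooled respiratory flag: sustained hypoxia, cyanosis, or withdrawal coded as respiratory, each patient counted once, with the same >15% definition. Describe it as a prompt for DSMB review and not as a stopping rule.
3. State that the 36-hour SaO2 capture and SAE counting continue after the FiO2 protocol is stopped.
4. Show the pooled flag to the DSMB with and without the withdrawal component, because that component arises essentially only in REOX II.
5. Align this with the DSMB Charter, or cite the charter if it already covers the point.

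The cost is a few sentences, two rows in the DSMB table and a coded reason for each withdrawal. The downside is more false flags, of the order shown in step 5, each leading to a DSMB discussion. No clinical rule changes.
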